“HEAT”

New Generation **H**ydrogel **E**ndovascular **A**neurysm treatment **T**rial

September 4, 2014
Protocol #1908: Version 07

A randomized controlled trial of new generation Hydrogel
coils versus bare platinum coils in the endovascular
treatment of intracranial aneurysms

Sponsor: **Northwestern University**
[name].
[name]
[name]
[contact]
[contact]

Funder: **MicroVention, Inc.**
[name]
[name]

This protocol contains confidential information for use by the Investigators and their designated representatives participating in this clinical investigation. It should be held confidential and maintained in a secure location. By accepting this document, you agree to maintain the information as confidential and to use it only for the purpose of conducting the study.

1 Protocol Synopsis

FULL STUDY TITLE	New Generation Hydrogel Endovascular Aneurysm Treatment Trial
STUDY OBJECTIVES	Comparing initial complete occlusion, recanalization, retreatment and adverse event rates of the HydroCoil® Embolic System to those of bare platinum coils.
STUDY DESIGN	International, randomized, prospective, controlled, multicenter trial
DEVICES	Second generation hydrogel coils from the HydroCoil® Embolic System™ (including the HydroSoft®, HydroFill® and HydroFrame® and future FDA and HPB approved Hydrogel coils) (“Hydrogel Group”) and Platinum coils (“Platinum Group”)
TREATMENT POPULATION	Subjects with intracranial aneurysms between the ages of 18 and 75 years inclusive
ESTIMATED TRIAL SIZE	600 randomized subjects
NUMBER OF SITES	Approximately 50 sites inside and outside of the U.S.
PRIMARY ENDPOINT	Aneurysm recurrence at any point during follow-up defined as any progression on the Raymond aneurysm occlusion scale.
SECONDARY ENDPOINTS	
• Packing density as measured by volumetric filling of the aneurysm• Clinical outcome at 18 to 24 months (mRS)• Peri-procedural and post-procedural adverse events related to the procedure and/or the device.• Mortality rate• Initial complete occlusion• Aneurysm retreatment• Hemorrhage from target aneurysm during follow-up• Aneurysm occlusion stability• Major vs. minor recurrence
VISIT SCHEDULE	Baseline, Procedure, 1 day post-procedure, 3 days to 28 days, 3 months to 12 months, 18 months to 24 months
PRINCIPAL INVESTIGATOR OF THE STUDY	[name]. [name] [name] [contact] [contact]

**CORE
LABORATORY
("CORE LAB")**

3.1 Hydrogel characteristics and the Hydrocoil Embolic System

The Hydrocoil Embolic System, developed and manufactured by MicroVention, Inc. (referred to in this Protocol as “MicroVention” or “Funder”), consists of porous hydrogel that either surrounds the platinum coil (as in the first generation of the HydroCoil Embolic System), or is surrounded by the platinum coil (as in the second generation of the HydroCoil Embolic System). Hydrogel consists of cross-linked hydrophilic copolymers. This material has been widely used in other medical applications (e.g. contact lenses and wound dressings). Hydrogel swells once exposed to the biological pH.

3.2 First Generation of the HydroCoil Embolic System: HydroCoil®

The first generation of the HydroCoil Embolic System is constructed using a core platinum coil surrounded by a sleeve of expandable hydrogel and an outer wire with gaps which allow expansion to occur. As such, the Hydrogel device is relatively stiff because of its dehydrated state, especially when compared to soft, platinum coils. The Hydrogel undergoes substantial swelling over time, markedly increasing its outer diameter and surface area over approximately 20 minutes. The increase in volume of the coil varies among the different HydroCoils. The HydroCoil 10 swells up to 0.022”, 5 times the volume of a platinum 10 coil; the HydroCoil 14 and HydroCoil 18 swell to 3 and 6 times the volume of Platinum 18 coils, respectively. The HydroCoil 14 and 18 coils swell up to 0.027” and 0.034”, respectively. Although substantial swelling is advantageous for aneurysm filling volume, there are limits associated with deployment time and size of the coils. Difficulty in deployment may lead to the need for multiple repositionings and potential untoward early swelling of the device which limits delivery through certain microcatheter systems. The HydroCoil is generally used as filling coils.

3.3 Second Generation of the HydroCoil Embolic System: HydroSoft®, HydroFrame®, HydroFill® and Future Hydrogel Products

In an attempt to offer a hydrogel coil as a soft finishing coil to allow ease in placing gel coils at the neck of the aneurysm, MicroVention developed the HydroSoft® line of embolic coils. These coils which are constructed with a filament of expandable hydrogel within the platinum coil are essentially as soft as platinum coils based on benchtop experiments and thus have handling properties similar to traditional platinum coils. Furthermore, since the hydrogel does not expand excessively, repositioning time is markedly prolonged to 30 minutes per the Instructions for Use (IFU). When fully hydrated, the HydroSoft swells up to approximately

0.013" to fill the gaps between the spirals of the platinum coil.^{7,9} The HydroSoft coils are primarily used as finishing or filling coils.

The next coil introduced by MicroVention, Inc., was HydroFrame®, a framing coil with hydrogel on the inside of the coil that is available in both 10 and 18 systems. MicroVention then developed HydroFill® which is used primarily as a filling coil, has a longer working time than HydroCoil (10 minutes in a .0165 microcatheter or 30 minutes in a .021 microcatheter), and swells to .018". The HydroFrame®, HydroSoft® and HydroFill® do *not* require steaming or prepping of the coil.

3.4 Studying the New Generation of the HydroCoil Embolic System

Studies to date on hydrogel coils have necessitated mixing hydrogel coils with platinum coils. With the introduction of the HydroFrame embolic coils, it is now possible to initiate a prospective randomized, multicenter trial to evaluate the effectiveness of packing an aneurysm *exclusively* with all Hydrogel coils compared to that exclusively with bare platinum coils. The question that remains unanswered is whether the new hydrogel technology improves results over traditional platinum coils.

For the purpose of this Protocol, subsequent references to the "HydroCoil Embolic System" refer specifically to the second generation of the HydroCoil Embolic System being utilized in this study and includes the HydroFrame®, HydroSoft®, HydroFill® and future FDA and HPB approved hydrogel products.

3.5 Previous Clinical Experience and studies of the HydroCoil and the Hydrocoil Embolic System

In early data from the prospective non-randomized HydroCoil for Endovascular Aneurysm occlusion (HEAL) study,¹⁰ the overall recurrence rate at 3 to 6 months was 28.1% (38/135 aneurysms). Further analysis of the data showed that when HydroCoil comprised 75% or more of total coil length the recurrence rate at 3 to 6 months dropped to 0% (0 out of 18 aneurysms). In contrast, when HydroCoil comprised less than 75% of total coil length, the recurrence rate was 23% (16 out of 71 aneurysms). Furthermore, when the last deposited coil was a HydroCoil, the recurrence rate was found to be 11% compared to 29% when the last deposited coil was a platinum coil. The difference was statistically significant. This difference in results, however, reflects one of the major limitations of the HEAL trial which was that no aneurysm was treated exclusively with HydroCoil.

In a prospective study, Gaba et al.¹¹ compared 50 aneurysms treated primarily with Hydrocoil (mean 71.8% based on coil length) to 57 volume- and shape-matched aneurysms embolized with bare platinum coils. The overall recurrence rate of the Hydrocoil treated aneurysms was 17% and compared favorably to those treated with bare platinum coils (24%) during a mean follow-up period of 12.3 months. These results also compare favorably to those reported by Murayama et al.¹² from their 11 year experience with bare platinum coils where the overall recanalization rate was 20.9%. Geyik et al.¹³ studied the recurrence rate in 35 bifurcation aneurysms, known for a higher tendency for recurrence, when treated with Hydrocoil and demonstrated an initial complete occlusion rate of 82.9% and at 6 months follow-up the overall recanalization rate was 11.4%.

Several other studies have examined hydrogel coils and the rates of initial complete occlusion have varied between 28% to 75% with recurrence rates between 11% and 28.1%.^{14,15} Tables 1 and 2 summarize the most relevant papers and their findings on occlusion rates, recanalization, retreatment, complications, morbidity and mortality rates. As a point of reference, the overall retreatment rate in the International Subarachnoid Aneurysm Trial (ISAT) was 17.4%, with an early retreatment rate of 8.8% and a late retreatment rate of 9.0%.¹⁶ The cut-off point between early and late retreatment was 3 months.¹⁶

Aneurysms showing the highest degree of occlusion and packing density (PD) are thought to be the best protected against recanalization and potential re-treatment.^{7,10,11,17-22} Cloft et al.⁹ studied the packing density of 11 aneurysms treated with HydroCoil compared to 11 historical controls that were treated with bare platinum coils. Most of these were small aneurysms (all 3.5-8.5mm) and mean packing density for the HydroCoil was found to be 73% versus 32% for bare platinum coils. Gaba et al.¹¹ calculated a theoretical volumetric percentage occlusion (VPO) and found that it was significantly higher in Hydrocoil than in inert bare platinum coils for all aneurysm sizes. The HydroCoil Endovascular Aneurysm Occlusion and Packing Study (HELPS) was a prospective, randomized, controlled trial that compared results from the HydroCoil system to results from bare platinum coils. The 500-patient, independently-run, multicenter, multinational 18-month trial was the first comparative study completed since the ISAT was presented in 2002. The angiographic results of the HELPS trial showed that there was a statistically significant decrease (8.6%) in major aneurysm recurrence rates in the HydroCoil system arm as compared to the bare platinum control arm.⁷

In addition to HELPS, one other trial is underway. The trial entitled "Patients Prone to Recurrence after Endovascular Treatment", or "PRET", is a large multi-center prospective randomized trial that aims to compare hydrogel coils and platinum coils in the treatment of large aneurysms that have a high-risk of recurrence. PRET intends to recruit 250 patients with large aneurysms (≥ 10 mm) and 250 patients with recurrent aneurysms at 23-40 centers. The clinical impact will be of major significance if substantial differences are found in the outcome of this randomized controlled trial. PRET was initiated prior to the development and introduction of the HydroFrame, however, which necessitated the mixing of hydrogel coils with platinum coils in the hydrogel group. With the development and introduction of the hydrogel framing coil (the HydroFrame) it will be possible to initiate a prospective randomized, multicenter trial to evaluate the effectiveness of packing an aneurysm *exclusively* with the HydroCoil® Embolic System (Hydrogel Group) with comparison to the current gold-standard of endovascular aneurysm treatment using bare platinum coils (Platinum Group).

4 Study Objectives

4.1 Study Hypothesis

The HydroCoil Embolic System allows for a higher packing density, higher initial occlusion, lower recanalization, and lower retreatment rates.

4.2 Primary Endpoint

The primary purpose of the HEAT study is to compare clinical and angiographic outcomes in patients receiving the HydroCoil Embolic System (Hydrogel framing, filling and finishing coils) versus patients receiving Platinum framing and filling coils. The primary outcome is aneurysm recurrence defined as any progression on the Raymond aneurysm occlusion scale anytime during follow-up (for further details, see section 6.4).

4.3 Secondary Outcomes

- Packing density as measured by the volumetric filling of the aneurysm
- Rate of initial complete occlusion
- Procedure and/or device-related morbidity and mortality
- Clinical outcome at 18 to 24 months as assessed using the modified Rankin Scale
- Re-treatment rates
- Hemorrhage from target aneurysm during follow-up
- Aneurysm occlusion stability
- Major versus minor recurrence

4.4 Safety Outcomes

- Peri-aneurysmal edema
- Aseptic meningitis
- Thromboembolic events
- Vasospasm
- Ventricular Enlargement
- Hydrocephalus
- Aneurysm Rupture
- Parent Vessel Occlusion

5 Clinical Study Design

5.1 Study Design

This is a randomized, controlled, multicenter, international post-market clinical trial. All devices used in this study are FDA and HPB (Health Protection Branch) approved. Eligible Subjects with intracranial aneurysms amenable to endovascular treatment and who consent to study participation will be randomly assigned 1:1 to either treatment arm:

- The HydroCoil Embolic System (“Hydrogel Group”), or
- Bare platinum coils (“Platinum Group”)

Both arms are standard of care. The patient will receive either Hydrogel or bare platinum coils in each respective arm. No other bioactive coils, including 1st generation coils or liquid embolics, can be utilized. In the Hydrogel arm, up to 10% of total coil length using bare platinum is allowed if deemed necessary by the investigator. Any type of bare platinum coil may be utilized. Assist-devices can be used at the discretion of the investigator.

5.2 Study Duration and Enrollment

The duration of the open enrollment phase will be 24 months or until the required number of patients are enrolled. Each patient will have a post-procedure follow-up of at least 18 months.

The number of Subjects to be enrolled, and randomized, in the study is up to 600. This sample size calculated to provide sufficient statistical power to show the anticipated difference in initial occlusion and recurrence rates between the 2 study arms (see section 9 for detailed statistical analysis). Patients will be recruited from up to 50 national and international centers. Each Investigational Site will be expected to enroll at least 20 Subjects. Each site must meet the eligibility criteria.

A multidisciplinary approach is expected from each qualified study center. The Neurovascular teams should include the appropriate specialties for the proper conduct of the study e.g., neurointerventionalist(s), experienced in intracranial aneurysm coiling, neurosurgeon(s), and study coordinator(s). In addition, the treating physician must meet a minimal level of expertise consisting of at least 5 successful intracranial aneurysm coiling procedures utilizing the HydroCoil Embolic system prior to enrolling patients into the study.

Each site must provide written approval from their reviewing Institutional Review Board (IRB) and all other required regulatory documentation prior to consenting and enrolling the first Subject.

5.3 Selection and Screening of Subjects

The study population for this clinical trial will be comprised of patients who have been diagnosed with intracranial aneurysms. In addition, these patients must satisfy all study inclusion and exclusion criteria. The trial will prospectively enroll and randomize up to 600 Subjects in a 1:1 ratio within only one stratification factor: participating site. The investigator or an approved member of the research team will review the patient's medical history for study eligibility and will fully inform any potential candidates about the purpose of the study. The difference between both types of coiling systems will be described and the potential risks and benefits will be explained in detail to each study candidate. Patients who voluntarily agree to participate in the trial will be asked to sign and date the Informed Consent Form (ICF). In the event a patient is unfit to provide signed informed consent (e.g. drowsy/confused), his/her Legally Authorized Representative (LAR) can sign the consent form. Once enrolled into the study, each participant will be assigned a study number. Patient names or identifiers will not be used on any study related documents. An electronic case report form (eCRF) will be completed at the end of each procedure and after each study related follow-up. Only the Principal Investigator of the study ([name]) and authorized members of the Sponsor including study monitors and auditors will have full access to the eCRF. Information from the eCRF will be entered into a secure, password protected study database. The Funder and its employees will have read-only access to collected eCRF study data, as provided by Northwestern, solely for review and adjudication of information related to any AE, SAE, ADE and UADE (as such terms are defined below) for legal and compliance purposes.

If a subject becomes pregnant while participating in this study, any angiographic follow-up will be done using non-contrast MRA as per standard of care.

5.3.1 Informed Consent

Prior to Subject participation in this study, the study team must obtain written IRB approval for the protocol and the Informed Consent Form (ICF). Once the patient's potential eligibility has been determined, the investigator or an IRB approved member of the research team will discuss the study and ask the patient if they are interested in participating in the study. The study will be explained to the patient in lay terms or at the level of patient understanding. The differences in coiling types will be explained in full detail. The approved ICF must be signed prior to performing study related assessments. The subject will be given a copy of the signed and dated ICF. The informed consent process must be documented and placed in the subject binder. Failure to obtain a signed ICF prior to the procedure constitutes a protocol deviation. It must be clear to subjects that they may withdraw from the study at any time and for any reason without penalty. It will be made clear to study participants that withdrawal from the study will not adversely affect their medical treatment and they will continue to receive therapy as indicated by their physician. Data from subjects obtained prior to withdrawal may be used for statistical analysis but no further data will be obtained.

5.3.2 Inclusion Criteria

Candidates for this study must meet the following criteria to be enrolled in the study (A "NO" answer excludes the subject):

1. Patient is between 18 and 75 years of age (inclusive).
2. Patient has a documented untreated intracranial saccular aneurysm 3-14 mm diameter angiographic lumen, ruptured or unruptured, suitable for embolization with coils.
3. For ruptured aneurysms, patients presenting with a Hunt and Hess Grade 1-3 or improving to such a grade before treatment.

4. Any type of bare platinum coils and HydroCoil Embolic System are treatment options (all shapes allowed).
5. Patient or next of kin or person with appropriate power of attorney has provided written informed consent.
6. Patient is willing and available for study follow-up visits.
7. Patient has not been previously entered into this Study.

5.3.3 Exclusion Criteria

Candidates will be ineligible for enrollment in the study if any of the following conditions apply (A "YES" answer excludes the subject):

1. Inability to obtain informed written consent.
2. Patient is < 18 or > 75 years old.
3. Target aneurysm is not saccular in nature (mycotic, fusiform, dissecting).
4. Target aneurysm is > 14 mm maximum luminal dimension, < 3 mm maximum luminal dimension.
5. Target aneurysm has been previously clipped or coiled.
6. Target aneurysm is in the physician's estimate unlikely to be successfully treated by endovascular techniques.
7. Patient has known hypersensitivity to platinum, nickel, stainless steel or structurally related compounds or hydrogel as found in the HydroCoil Embolic System and/or bare platinum coils.
8. Baseline Hunt and Hess scale 4 or 5 for ruptured aneurysms.
9. Intended use of a flow diverting stent (e.g. pipeline)
10. Subject has concurrent intracranial pathology, e.g.
 - Moyamoya disease
 - Vasculitis documented by biopsy results
 - AVMs
 - AV fistulas
 - Significant atherosclerotic disease (i.e. symptomatic and or >50% narrowing of the parent arteries necessary to traverse in order to coil the target aneurysm)
 - Intracranial Hematoma (unrelated to the target aneurysm)
 - Brain tumors
 - Vascular tortuosity and other conditions preventing access to target aneurysm
11. Subject has serious co-morbidities that could confound the study results:
 - Uncontrolled hypertension
 - Uncorrectable coagulation abnormality
 - Contraindications for heparin, aspirin or clopidogrel
 - Uncontrolled Diabetes Mellitus
 - Organ failure of kidney, liver, heart, or lung

- Myocardial infarction within the past 6 months
 - Cancer likely to cause death within 2 years or less.
12. Subject history indicates high risk of non-compliance (e.g., substance abuse, psychosocial issues, etc.)
 13. Subject has a known history contraindicating contrast dye or iodine that cannot be pre-medicated prior to coiling procedure (vs. sensitivity which can be safely controlled by antihistamine, steroid, etc.). Medical clearance will be needed for this issue.
 14. Patients who are unable to complete scheduled follow up assessments at the enrolling center due to limited life expectancy (<2 years), co-morbidities or geographical considerations
 15. Subject is currently breast feeding, pregnant or plans to become pregnant in the next 2 years.
 16. Major surgical procedure or trauma within 30 days prior to randomization.
 17. The patient is currently enrolled in another clinical study (device or drug).
 18. More than one aneurysm needs to be treated at the same time.

6 Subject Enrollment, Procedures, and Follow-Up

6.1 Screening and Consent

Eligibility will be assessed once the neurovascular team makes a decision on endovascular treatment of an aneurysm. A local site log of all eligible patients will be kept and a copy returned to the coordinating site (Northwestern University) when requested by the study monitor.

If a patient fulfills the inclusion and exclusion criteria, an authorized member of the research team will discuss the trial and provide the patient or his/her LAR with the informed consent form. The patient or LAR will be provided adequate time to consider participation in the trial and the research team will answer all questions regarding the trial. A copy of the consent will be retained in the patient's medical record, one will be given to the patient, and the original will be retained by the local site.

All patients who meet the eligibility criteria and give written informed consent are eligible for enrollment into the study which occurs at the time of randomization

Screen failures are defined as a subject consented and screened for enrollment, but not ultimately enrolled on the day of randomization; provided that the failure to enroll was attributable to the subject's failure to meet the inclusion or exclusion criteria listed in the protocol.

Screen failures and subjects who electively withdraw from the study will be dropped from any further follow-up and statistical analysis of this study. The original ICF and any data collected up until the date of withdrawal will be maintained in the clinical site's study files and their number will not be used again in the study.

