6.13 Study Completion

Once a subject completes all study follow-up visits which include the 18 to 24 month visit, the Final Follow-Up eCRF must be completed. During the course of the study, it is possible that subjects will be

withdrawn from the study prior to completing the final 18 to 24 months visit. Factors leading to Subject withdrawal may include, but are not limited to the following:

- **Subject Withdrawal** - A Subject may voluntarily withdraw from the study at any time for any reason, whether disclosed or undisclosed, without affecting their future medical treatment or benefits. In addition, if a patient refuses follow-up examinations and evaluations the investigator may remove her/him from the study after appropriate notice.
- **Subject Lost to Follow-Up** – If the subject does not show up to the planned follow-up visits, attempts should be made to contact her/him. If after at least three (3) attempts the subject remains unreachable, she/he may be withdrawn from the study. The research team must document at least three contact attempts before declaring a subject as lost to follow-up.
- **Subject Death** - When a Subject dies, the ADVERSE EVENT and STUDY EXIT eCRFs must be completed immediately (within 24 hours of the event). If available, documents such as the death summary, the autopsy report and a copy of the death certificate shall be provided to the principal investigator of the site and the Sponsor, Northwestern University, and the funder, MicroVenton. Personal identifiers should be removed from any documentation provided. The site's IRB shall also be notified promptly.

If a subject was withdrawn for any of the above mentioned reasons, the Study Exit eCRF form must be completed.

7 Management of Adverse Events

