8.2 IRB Approval

The Investigator or the study coordinator is responsible for submitting the study protocol and any changes issued by the Sponsor during the course of the study for IRB approval prior to any Subject enrollment and amendments taking effect as well as obtain renewals at periods determined by the IRB for the duration of the study.

9 Statistical Methods

Primary analysis of primary and secondary outcomes will be based on the intent-to-treat (ITT) principle. Secondary analyses will examine differences based on per protocol principles, as well as a detailed analysis of missing data, should there be any (see below).

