9.2 Statistical Analysis Plan

9.2.1 Primary endpoints:

Chi-square tests (simple logistic regression) will be used to determine if rates of recurrence differ by coil type. Additionally, multiple logistic regression models will be used to examine those rates while adjusting for various covariates, including, but not limited to: site, age, gender, aneurysm size, neck size, packing density and rupture status. Models will be fit to examine potential interactions between covariates and randomization group in predicting outcomes; and final models will be fit depending on statistical and clinical significance of the covariates to the outcome as well as any change in the relationship between the randomization group and outcome. Analyses will be presented both as univariate and adjusted Odds Ratios and corresponding [Wald] 95% Confidence intervals.

While the study has been designed to minimize any missing data due to this being a longitudinal study, the potential for missing data or loss to follow-up is present. Patterns of missing data and dropout will be examined to determine if complete case analysis or available data analyses are appropriate or if imputation methods will need to be incorporated. Should a complete case analysis be appropriate, PROC LOGISTIC will be used to analyze these binary outcomes; otherwise PROC GLIMMIX will be used for an available data analysis. If imputation methods are called for, PROC MI and PROC MIANALYSE will be used and results presented. All analyses will be run at a type I error rate of 5% using SASv9.2, Cary, NC.

9.2.2 Secondary endpoints:

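### Section 6.1 removes randomised subjects who later withdraw from the statistical analysis, against the ITT primary analysis in Section 9 and the dropout handling in 9.2.1

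*Combined protocol and SAP*

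**What the plan says.** Five places in the combined protocol and SAP bear on what happens to a subject who withdraws.

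- **Section 6.1 (Screening and Consent):** "Screen failures and subjects who electively withdraw from the study will be dropped from any further follow-up and statistical analysis of this study". The same section puts enrolment at randomisation ("eligible for enrollment into the study which occurs at the time of randomization"). On the records of these subjects it says: "any data collected up until the date of withdrawal will be maintained in the clinical site's study files and their number will not be used".
- **Section 6.13 (Study Completion):** "A Subject may voluntarily withdraw from the study at any time for any reason, whether disclosed or undisclosed". Loss to follow-up and death are listed as separate reasons for exit.
- **Section 5.3.1 (Informed Consent):** "Data from subjects obtained prior to withdrawal may be used for statistical analysis but no further data will be obtained".
- **Section 9 (Statistical Methods), opening paragraph:** "Primary analysis of primary and secondary outcomes will be based on the intent-to-treat (ITT) principle".
- **Section 9.2.1 (Primary endpoints):** "Patterns of missing data and dropout will be examined to determine if complete case analysis or available data analyses are appropriate", with imputation as the third option.

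The primary outcome in Section 4.2 is "any progression on the Raymond aneurysm occlusion scale anytime during follow-up".

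**The concern.** Section 6.1 sets an analysis rule that depends on something that happens after randomisation. Applied as written, it takes a randomised, treated and imaged patient out of the analysis because that patient later chose to leave. An ITT analysis is meant to prevent this.

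The endpoint makes the problem concrete. Progression at any time counts, so progression on the 3 to 12 month scan fixes the outcome as a recurrence. No later information can change it. Under 6.1 that known event disappears if the patient withdraws before the 18 to 24 month visit. On the same literal reading, packing density, initial occlusion and procedural safety data go too, although all are known at or soon after the procedure.

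The exclusion need not be neutral between arms. Operators know the coil type, site investigators grade occlusion themselves (6.4), and no blinding of patients is described. Withdrawal after a known scan result could therefore differ by arm, and the bias could go either way. Two analysts, one following 6.1 and the other Section 9, would report the primary endpoint on different populations.

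**Working it through.** **1. Does 6.1 reach randomised subjects?**

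- It refers to further follow-up and to data collected up to a date of withdrawal. Both fit people already in the study.
- It says the subject's number is not reused. Section 6.3 has the EDC issue the study number at randomisation, and the documents describe no separate screening number.
- Screen failures are defined in 6.1 as people not ultimately enrolled, so elective withdrawers are a second, distinct group.
- No sentence limits the rule to the interval between consent and randomisation.

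**2. Set against the other sections**

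| Section | Treatment of a randomised subject with a recurrence at 3 to 12 months who then withdraws |
|---|---|
| 6.1 | Out of the statistical analysis |
| 5.3.1 | Data up to withdrawal may be used (permitted, not required) |
| 9 | In, under ITT |
| 9.2.1 | In: the outcome is observed, so even a complete-case analysis keeps it |

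**3. The plan's own figure**

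Inputs from Section 9.1 and Table 5: recurrence 33.0% versus 22.8%, two-sided 5% chi-square test, 1:1, N = 600, 80% power. The pooled-variance two-proportion formula without continuity correction gives 303 per arm (606 in total), and power of 79.7% at 300 per arm. The planned figure is reproduced, so these rates are a fair base for a sensitivity check.

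**4. Sensitivity of the primary comparison**

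Baseline events: 0.33 × 300 = 99 and 0.228 × 300 = 68.4, rounded to 68. Excluding k observed recurrences from an arm with e events changes its rate from e/300 to (e − k)/(300 − k). The first exclusion moves the rate by (1 − p)/299:

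- platinum: 0.67/299 = 0.22 points
- hydrogel: 0.772/299 = 0.26 points

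The p-values come from the two-sided pooled z test without continuity correction, which equals the chi-square test. The counts k are assumptions, because the documents give no withdrawal rate.

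| Recurrences excluded | Platinum | Hydrogel | Difference (points) | p |
|---|---|---|---|---|
| None | 99/300 = 33.0% | 68/300 = 22.7% | 10.3 | 0.0048 |
| 5 platinum | 94/295 = 31.9% | 22.7% | 9.2 | 0.0117 |
| 10 platinum | 89/290 = 30.7% | 22.7% | 8.0 | 0.0275 |
| 13 platinum | 86/287 = 30.0% | 22.7% | 7.3 | 0.0445 |
| 14 platinum | 85/286 = 29.7% | 22.7% | 7.1 | 0.0520 |
| 5 hydrogel | 33.0% | 63/295 = 21.4% | 11.6 | 0.0014 |
| 10 hydrogel | 33.0% | 58/290 = 20.0% | 13.0 | 0.0004 |
| 5 in each arm | 94/295 = 31.9% | 63/295 = 21.4% | 10.5 | 0.0039 |

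Power lost because subjects leave before any follow-up imaging is not counted here. No analysis rule recovers those outcomes.

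**The case against.** The best case against is that Section 9 governs the analysis, 5.3.1 points the same way, and 6.1 is one administrative sentence under a screening heading. A statistician would normally work from Section 9. The word *further* could also govern both follow-up and analysis, which would bring the sentence close to 5.3.1.

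The heading does make a pre-randomisation intent possible, but the text does not state it and its details point to randomised subjects. The reading of *further* does not help: the main analysis takes place after withdrawal, so the subject is still excluded from it. No section gives Section 9 precedence or defines the ITT population as all randomised subjects.

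The points on scale are fair and stand:

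- Only elective withdrawal is covered, not death or loss to follow-up.
- The 14-event case is one-sided. It is 14/300 = 4.7% of the platinum arm but 14/99 = 14% of its recurrences, with no hydrogel recurrence and no recurrence-free subject excluded.
- If 10% of patients with recurrence withdrew in both arms, the rates would be (99 − 9.9)/(300 − 9.9) = 30.7% and (68 − 6.8)/(300 − 6.8) = 20.9%, a difference of 9.8 points with p = 0.007.
- The Core Lab is blinded to coil type (6.5), and nothing in the documents shows that withdrawal differs by arm.
- The exclusion is reversible: data stay in site files and are entered in the study database within 5 days of each visit (Sections 11 and 12.2).

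These points limit the likely size. They do not remove the contradiction about who is in the primary analysis.

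**Conclusion.** The concern holds. As written, 6.1 excludes randomised subjects on a post-randomisation event and conflicts with Section 9 and 9.2.1. It is also in tension with 5.3.1, which allows the use of pre-withdrawal data without requiring it. The textual conflict does not depend on any assumption.

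The numerical effect does, and it cannot be derived from the documents. At the planned rates, each observed recurrence excluded lowers its arm's rate by about 0.22 to 0.26 points. One-sided loss can shrink or inflate the treatment difference, while balanced loss leaves it close to 10 points. The matter should be settled before outcome data are seen, because otherwise the primary population becomes a post-hoc choice. It is a must-fix because it decides who is analysed for the primary endpoint, not because a large bias has been shown.

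**What to change.** In Section 6.1:

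- Limit exclusion from statistical analysis to screen failures and others who were never randomised.
- State that every randomised subject stays in the ITT population.
- State that nothing further is collected after withdrawal, but that everything observed before it is analysed: recurrence, retreatment, hemorrhage, adverse events, packing density and initial occlusion.
- Refer to 9.2.1 for outcomes missing after withdrawal, using the available-data analysis or imputation that section provides.

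In Section 5.3.1, change the permission to use pre-withdrawal data into a statement that these data will be used, so that it matches.

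The cost is a minor wording amendment to two sections, with no new data or visits. The downside is that some subjects with missing outcomes stay in the ITT set and must be dealt with under 9.2.1.
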